2.2.3 Exploratory & Subgroup Analyses

Exploratory and subgroup analyses may be performed using the same methodology as for primary and secondary outcomes.

2.3 Safety Analysis

2.3.1 Adverse Events

For adverse events, a descriptive analysis will be conducted. Adverse events will be presented in a frequency table by System Organ Class (SOC), Preferred Term (PT), Lower Level Term (LLT) and study group. Furthermore, the lower level term, intensity, relationship, action taken, and outcome will be reported for each adverse event. Lastly, a summary of adverse events that are possibly or probably related to the study product will be presented.

The proportion of at least one adverse event when taking RiaGev™ or comparator at pre-supplementation and post-supplementation will be assessed using a Chi Square or Fisher’s Exact test as appropriate.

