6 STUDY DESIGN

This will be a randomized, double-blind, comparator-controlled, crossover, safety and efficacy study conducted at Prism Clinical Research Clinic, Saint Paul, MN, USA, a KGK Science Inc. partner.

The planned sample size for this study is 18, crossing over once is equivalent to 36 participants. To evaluate the outcomes, study assessments will be conducted as per the schedule of assessments in section 1.3

Study Arm	Number of Participants
RiaGev [™] → Comparator	N = 9
Comparator→ RiaGev [™]	N = 9
Total	N = 18

investigate the safety and efficacy of RiaGev[™] in healthy adults

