1.5 Safety Outcomes

1. Incidence of pre-emergent and post-emergent adverse events when supplemented
2. Vital signs (blood pressure (BP) and heart rate (HR)) when supplemented
3. Clinical chemistry (alanine aminotransferase (ALT), aspartate aminotransferase (AST), total bilirubin, creatinine, electrolytes (Na, K, Cl), fasting glucose and estimated glomerular filtration rate (eGFR))
4. Hematology (white blood cell (WBC) count with differential (neutrophils, lymphocytes, monocytes, eosinophils, basophils), red blood cell (RBC) count, hemoglobin, hematocrit, platelet count, RBC indices (mean corpuscular volume (MCV), mean corpuscular hemoglobin (MCH), mean corpuscular hemoglobin concentration (MCHC), red cell distribution width (RDW))

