1.8 Study Design, Visit Breakdown and Schedule of Assessment

This is a randomized, double-blind, comparator-controlled, crossover study to evaluate safety and efficacy conducted at Prism Clinical Research Clinic, Saint Paul, MN, USA, a KGK Science Inc. partner.

A total of 18 participants were enrolled in the study. The allocation of participants is provided in **Table 1**. The schedule of visits is presented in **Figure 1**. The schedule of assessments is described in **Table 2**.

A randomized, double-blind, comparator-controlled, cross-over study to investigate the safety and efficacy of RiaGev™ in healthy adults

Table 1. Allocation of participants

Study Arm	Number of Participants
RiaGev™ → Comparator	N = 9
Comparator → RiaGev™	N = 9
Total	N = 18

Figure 1. Study design

[figure not shown]

Table 2. The schedule of assessments

Procedures/assessments	Visit 1 Screen	Visit 2 Day 1 (+1 Day)	Visit 3 Day 3 (+1 Day)	Visit 4 Day 5 (+1 Day)	Visit 5 Day 8 (+1 Day)	Visit 6 Day 1 (+1 Day)	Visit 7 Day 3 (+1 Day)	Visit 8 Day 5 (+1 Day)	Visit 9 Day 8 (+1 Day)
Informed consent	X								
Review inclusion/exclusion criteria	X	X							
Review medical history	X								
Review concomitant therapies	X	X	X	X	X	X	X	X	X
Vitals: Height*, weight, heart rate, blood pressure *Height will only be measured at Visit 1	X	X	X	X	X	X	X	X	X
Urine pregnancy test	X	X							
Electrocardiogram (EKG)	x								
Physical examination	X	X							X

A randomized, double-blind, comparator-controlled, cross-over study to investigate the safety and efficacy of RiaGev™ in healthy adults

Procedures/assessments	Visit 1 Screen	Visit 2 Day 1 (+1 Day)	Visit 3 Day 3 (+1 Day)	Visit 4 Day 5 (+1 Day)	Visit 5 Day 8 (+1 Day)	Visit 6 Day 1 (+1 Day)	Visit 7 Day 3 (+1 Day)	Visit 8 Day 5 (+1 Day)	Visit 9 Day 8 (+1 Day)
Randomization		X							
CBC, electrolytes (Na, K, Cl), HbA1c*, fasting glucose, eGFR, creatinine, AST, ALT, and total bilirubin *HbA1c will only be measured at Visit 1	X				X	X			X
Maximum heart rate (HR _{max}) treadmill test	X								
Skin fluoroscopy for NADH analysis (optional)		X			X	X			X
Blood Collection for NAD+ analysis		X	X	X	X	X	X	X	X
Blood Collection for GSH/GSSG and ATP/AMP analyses		X			X	X			X
OGTT: glucose and insulin T= 0, 15m, 30m, 45m, 60m, 90m, 2h		X			X	X			X
Questionnaire		X	X	X	X	X	X	X	X
Treadmill Exercise protocol		X			X	X			X
Salivary Collection Kit Dispensed	X	X	X	X	X	X	X	X	
Salivary Collection Kit Returned		X	X	X	X	X	X	X	X

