2.1.2 Treatment Exposure and Compliance

Number of dosage units taken will be assessed by counting the number of returned unused test product(s) at each visit and subtracting this from the total number of dosage units dispensed. Compliance will be calculated by determining the number of dosage units taken divided by the number of dosage units expected to have been taken, multiplied by 100.

$$\frac{\text{number of dosage units taken}}{\text{number of dosage units expected to have been taken}} \times 100\%$$

Possible differences in compliance between the study groups at the end of each treatment will be assessed using a Mixed Model. The model will include treatment, sequence and period as fixed effects and subject as a random effect.

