2.2 Effectiveness/Efficacy analysis

2.2.1 Primary Outcome:

The primary outcome is the change in whole blood NAD⁺ levels from baseline to day 8 when supplemented with RiaGev™ or comparator.

The primary null hypothesis is as follows:

H₀: There is no significant difference in mean change in NAD⁺ level from pre-supplementation to post-supplementation, between subjects taking RiaGev™ or comparator.

Possible differences before exercise from day 1 to days 3, 5 and 8 between the study groups will be assessed using repeated-measures mixed ANCOVA. The model will include treatment, visit number, sequence and period as fixed effects and subject as a random effect. Between group p-values will be obtained from this model, while within group p-values will be obtained using paired t tests or Wilcoxon Signed Rank test as appropriate.

Possible differences at after exercise from day 1 to day 8 between the study groups will be assessed using repeated-measures mixed ANCOVA. The model will include treatment, visit number, sequence and period as fixed effects and subject as a random effect. Between group p-values will be obtained from this model, while within group p-values will be obtained using paired t tests or Wilcoxon Signed Rank test as appropriate.

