4. The change in salivary cortisol after a 7-day supplementation with either RiaGev™ or comparator	Interval	Repeated-measures mixed ANCOVA
5. The change in Checklist Individual Strength (CIS) Questionnaire outcome after a 7-day supplementation with either RiaGev™ or comparator	Interval	Repeated-measures mixed ANCOVA
Safety Outcomes		
1. Proportion of participants experiencing at least one adverse event when taking RiaGev™ or comparator	Nominal	Chi Square or Fisher's Exact Test
2. The effect of supplementation with RiaGev™ or comparator on vital signs (blood pressure and heart rate) and anthropometrics (weight and BMI) from pre-supplementation to Day 7 post-supplementation a. blood pressure (BP) b. heart rate (HR)	Interval Interval	Not applicable
3. The effect of supplementation with RiaGev™ or comparator on clinical chemistry from screening to end-of-study as assessed by a. alanine aminotransferase (ALT) b. aspartate aminotransferase (AST) c. total bilirubin d. creatinine e. sodium (Na)	Interval Interval Interval Interval	Not applicable

Outcome	Data type	Between groups analysis methods

 f. potassium (K) g. chloride (Cl) h. fasting glucose i. estimated glomerular filtration rate (eGFR) 	
 Interval Interval Interval Interval Interval 	

4. The effect of supplementation with RiaGev™ or comparator on hematology from screening to end-of-study as assessed by
 
 a. white blood cell (WBC) count b. neutrophils c. lymphocytes d. monocytes e. eosinophils f. basophils g. red blood cell (RBC) count h. hemoglobin i. hematocrit j. platelet count k. mean corpuscular volume (MCV) l. mean corpuscular hemoglobin (MCH) m. mean corpuscular hemoglobin concentration (MCHC) n. red cell distribution width (RDW) 	
 Interval Interval Interval Interval Interval Interval Interval Interval Interval Interval Interval Interval Interval Interval Interval 	Not applicable
Demographic Characteristics & Other Outcomes		
1. Age	Interval	Not applicable
2. Gender	Nominal	Not applicable
3. Ethnicity	Nominal	Not applicable
4. Overall Compliance	Interval	ANOVA

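### The adverse-event test treats 18 crossover participants as two independent groups, and the related-event summary leaves out the strongest causality grade

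*SAP*

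**What the plan says.** SAP 2.3.1 opens with a descriptive adverse-event analysis and then adds a test: the proportion with at least one event on RiaGev or "comparator at pre-supplementation and post-supplementation will be assessed using a Chi Square or" Fisher's Exact test. In SAP Table 3 the same outcome reads "Proportion of participants experiencing at least one adverse event when taking" either product, with the between-groups method "Chi Square or Fisher's Exact Test". The safety outcome listed in SAP 1.5 is "Incidence of pre-emergent and post-emergent adverse events when supplemented".

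The design is a crossover with 9 people per sequence. SAP 1.8 states "A total of 18 participants were enrolled in the study", while protocol 6 remarks that "crossing over once is equivalent to 36 participants". Elsewhere the SAP allows for the design. For compliance (2.1.2), "The model will include treatment, sequence and period as fixed effects and subject as a random effect". For the primary outcome (2.2.1), "The model will include treatment, visit number, sequence and period as fixed effects and subject as a random effect". The secondary outcomes in 2.2.2 follow the same pattern.

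Protocol 11.3.2 plans description only for adverse events. Protocol 11.3 has a general sentence assigning Chi-squared or Fisher's Exact tests to categorical variables. SAP 2.3.1 also promises a summary of events judged possibly or probably related; protocol 10.1.1 has a further grade above these, Most probable.

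**The concern.** Chi Square and Fisher's Exact compare two separate sets of people. Here one set supplies both columns, apart from anyone who leaves after one period. Allowing a choice between the two tests does not help, because neither is paired, and neither allows for period.

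The contrast is also unclear. SAP 2.3.1 brings in a before-and-after element that Table 3 lacks. On any reading both proportions come from the same people, so the mismatch remains. Neither text says where washout events belong. They can be expected: protocol 9.7 has a 7-day washout, and in protocol 9.8 adverse events are reviewed at visit 6 before the second product is dispensed.

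Safety is a named objective, and this is the only inferential safety comparison, since Table 3 marks vital signs, chemistry and hematology as not applicable. A non-significant result from a test that does not fit the design could be read as reassurance. Separately, a related-event summary that omits the strongest grade would understate relatedness.

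**Working it through.** **1. The plan's own sample size relies on pairing.** Inputs from protocol 11.1: difference 8.7, SD 11.04, 5% two-sided (assumed), 80% power, 20% loss. Taking 11.04 as the SD of the within-person difference, n = (11.04 × (1.960 + 0.842) / 8.7)² = 12.6, so 13; 13/0.8 = 16.25, so 17. With the t distribution n = 15; 15/0.8 gives 19 and 15 × 1.2 gives 18. A parallel-group reading needs 26 per arm. The stated 18 therefore fits a paired calculation.

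**2. What the planned tests drop.** With event rates p1, p2 and within-person correlation r,

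Var(difference) = [p1(1−p1) + p2(1−p2) − 2r√(p1(1−p1)p2(1−p2))] / n.

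The independent-groups tests omit the last term. At equal rates of 0.3 and r = 0.3 the bracket is 0.42 − 0.126 = 0.294, while the tests use 0.42, which is 1.43 times too large.

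**3. Same margins, different pairing.** Take 10/18 v 4/18 (invented). Fisher is 0.086 and uncorrected Chi Square 0.040 in every row. Exact McNemar is 2 × P(X ≤ smaller discordant count), with X binomial on the discordant pairs at 1/2. For 6 v 0 this is 2/64 = 0.031; for 7 v 1 it is 2 × 9/256 = 0.070. The mid-p version subtracts P(X = smaller count).

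| Events on both products | Discordant | Exact McNemar | Mid-p |
|---|---|---|---|
| 4 | 6 v 0 | 0.031 | 0.016 |
| 3 | 7 v 1 | 0.070 | 0.039 |
| 2 | 8 v 2 | 0.109 | 0.065 |
| 1 | 9 v 3 | 0.146 | 0.092 |
| 0 | 10 v 4 | 0.180 | 0.118 |

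The Tango score 95% interval for the difference of 6/18 = 0.33 is 0.10 to 0.56 with 4 shared, −0.01 to 0.60 with 2, and −0.07 to 0.64 with none.

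**4. Error rates.** Rates and correlations are assumed. Exact enumeration over 18 pairs, with P(event on both) = p1p2 + r√(p1(1−p1)p2(1−p2)), rejecting at p ≤ 0.05. Mainland-Gart is enumerated with 9 per sequence. Columns are r = 0 / 0.3 / 0.5.

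| Test | Type I error, both rates 0.3 | Power, 0.5 v 0.2 |
|---|---|---|
| Fisher | 0.022 / 0.007 / 0.002 | 0.359 / 0.331 / 0.300 |
| Chi Square, uncorrected | 0.050 / 0.020 / 0.007 | 0.498 / 0.493 / 0.483 |
| Exact McNemar | 0.018 / 0.010 / 0.004 | 0.318 / 0.400 / 0.466 |
| Mid-p McNemar | 0.038 / 0.028 / 0.015 | 0.424 / 0.545 / 0.667 |
| Mainland-Gart | 0.012 / 0.004 / 0.001 | 0.271 / 0.292 / 0.270 |

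At 0.3 v 0.1 and r = 0 / 0.3, pairing gains nothing: mid-p 0.250 / 0.277 against Chi Square 0.317 / 0.281, and exact McNemar 0.150 / 0.148 against Fisher 0.205 / 0.160.

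For dropout, 18 × 0.8 = 14.4, taken as 14 pairs plus 2 one-period people per product who enter only the unpaired tests. At 0.5 v 0.2, mid-p is 0.318 / 0.379 / 0.416 against Chi Square 0.451 / 0.440 / 0.426, and exact McNemar 0.210 / 0.227 / 0.219 against Fisher 0.281 / 0.251 / 0.222.

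**5. Causality grades.** Protocol 10.1.1 has five: Most probable, Probable, Possible, Unlikely, Not related. The SAP summary names the second and third only. Read literally, the first drops out.

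**The case against.** The strongest reply concerns weight. SAP 2.3.1 is mainly descriptive, the test is one added sentence with no decision attached, and its error is conservative under positive correlation. That stands, and it keeps the point minor.

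Nor is a paired test clearly better at this size. Mainland-Gart, which allows for period, is more conservative than Fisher and has less power at 0.5 v 0.2. With dropout, or at low rates and low correlation, the McNemar versions can have less power than the planned tests. No operating characteristics were computed for a logistic mixed model with 18 people. This also stands. It means the case rests on fit to the design, not on power, and it favours dropping the test over replacing it.

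The SAP does not say whether Chi Square is continuity-corrected. If it is, 10/18 v 4/18 gives 0.087, close to Fisher, and if Fisher were used for sparse tables the uncorrected power figures would overstate the plan's at low rates. Either way, the p-value still ignores the pairing.

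The general sentence in protocol 11.3 gives the test some footing, but it names the same two unpaired tests and so does not resolve the mismatch. Finally, Most probable events may be rare, since that grade refers to rechallenge and none is scheduled, and they remain in the event-level report. The omission is a small correction, but a real one.

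**Conclusion.** The concern holds. The named tests do not fit a crossover on any reading of the contrast, and the SAP's own efficacy and compliance models show the structure that is missing. In the example, the paired p-value ranges from 0.031 to 0.180 while the planned ones stay fixed. Under assumed null rates of 0.3, the planned tests' type I error falls to 0.007 (Fisher) and 0.020 (Chi Square) at correlation 0.3. All these sizes rest on assumed rates and correlations, because the documents give none. The gap in the related-event summary is independent of this and follows from the text alone. The change should be made, but the impact is minor: the descriptive tables carry the safety assessment and the primary outcome is not affected.

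**What to change.** - **Test.** Delete the test sentence in SAP 2.3.1 and mark Table 3 Safety Outcome 1 as not applicable, like the other safety outcomes. Describe events by product for the whole Safety Population, and give the paired difference in proportions with its 95% interval for those observed on both products.
- **If a test is kept.** Use a paired method that allows for period: Mainland-Gart, Prescott, or a logistic mixed model with treatment and period fixed and subject random, with a named fallback for non-convergence. Mid-p McNemar is simpler but ignores period.
- **Contrast.** State that events in the RiaGev period are compared with events in the comparator period, report pre-emergent events descriptively, and say to which period washout events belong.
- **Related events.** Extend the summary to possibly, probably or most probably related.

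The cost is wording edits, with no new data. Description only gives up a p-value that protocol 11.3.2 did not plan; a line should say that the general categorical-test sentence in protocol 11.3 does not extend to adverse events. If a test is kept, McNemar, Mainland-Gart and Prescott leave out people seen in one period only, and power may fall below that of the planned tests; the mixed model keeps those people.

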2.3.2 Other Safety Variables

Clinically significant measurements for the variables listed below will be discussed as part of the final study report.

1. Vital signs (blood pressure (BP) and heart rate (HR))
2. clinical chemistry (alanine aminotransferase (ALT), aspartate aminotransferase (AST), total bilirubin, creatinine, electrolytes (Na, K, Cl), fasting glucose and estimated glomerular filtration rate (eGFR))
3. hematology (white blood cell (WBC) count with differential (neutrophils, lymphocytes, monocytes, eosinophils, basophils), red blood cell (RBC) count, hemoglobin, hematocrit, platelet count, RBC indices (mean corpuscular volume (MCV), mean corpuscular hemoglobin (MCH), mean corpuscular hemoglobin concentration (MCHC), red cell distribution width (RDW))

2.4 Statistical and Analytical Issues

2.4.1 Handling of Dropouts and Missing Data

Missing values in the intention-to-treat analysis will be imputed using the last available value (“last-observation-carried-forward” (LOCF)) or multiple imputation methods as appropriate. No imputation will be performed for missing values in the per protocol or the safety populations.

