8.5 Directions

Participants will be instructed to take two doses of the IP daily, once in the morning and once in the evening. Each dose will be 3 capsules, one dose will be administered immediately before breakfast and the other dose will be administered immediately before dinner. In both study periods, on day 1 only the evening dose will be administered and on day 8 only morning dose will be administered. The Clinic staff will instruct participants to save all unused and open packages and return them to Prism Clinical for a

determination of compliance. If a dose is missed participants are instructed to consume the missed dose anytime on the same day, except at bedtime. Participants will be advised not to exceed two servings daily.

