11.3 Statistical Analysis Plan

The primary outcome is the change in whole blood NAD+ levels from baseline to day 6 compared between $RiaGev^{TM}$ and comparator.

An effectiveness analysis based on the intent-to-treat population and an efficacy analysis based on the per protocol population will be performed. Safety analysis will be done for the safety population.

Variables will be tested for normality and transformed to the log scale if found to be non-normally distributed. Log-normally distributed variables will be analyzed in the logarithmic domain. Intractably non-normal outcome variables will be analyzed by appropriate non-parametric tests.

Missing values in the intent-to-treat and per protocol analyses will be imputed using the most recent previously-available value (LOCF, or "last-observation-carried-forward" imputation) or multiple imputation methods. No imputation will be performed for missing safety values.

For each continuous endpoint, a summary table will be prepared with a variety of summary statistics including mean, standard deviation, median and range values for each time point-treatment pairing. To account for any a priori differences between groups, the summary statistics of the changes from baseline will also be provided. For parameters requiring a logarithmic transformation, the summary statistics will be provided as non-transformed values. Mean values will be displayed as graphs, with a separate line for each product, and error bars indicating standard errors or standard deviations. Mean changes from baseline will be graphed similarly. Although imputed data will be used for significance testing, non-imputed data will be used for presenting summaries. Categorical variables will be summarized as counts and percentages.

Continuous efficacy endpoints will be tested for significance between groups by Analysis of Covariance (ANCOVA). The dependent variable will be the measurement at each visit, the factor will be the treatment group, and the value at baseline (Day 1) will be the covariate. A within group analysis on effectiveness/efficacy endpoints will be done using the Student's paired t-test or, in the case of intractable non-normality, the Wilcoxon sign rank test. Categorical variables will be compared using Chi-squared or Fisher's Exact tests as appropriate.

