1.9 Study Populations

A total of three populations are defined for all summaries and analyses. Subjects who have satisfied the population criteria will be classified in the designated population.

Intent-to-Treat (ITT) Population

The ITT population consists of all subjects who received either product, and on whom any post-randomization efficacy information is available. The ITT population will be used to present all the effectiveness information according to the treatment to which subjects were randomised.

Per Protocol (PP) Population

The PP Population consists of all subjects who consumed at least 80% of treatment or placebo doses, did not have any major protocol violations and completed all study visits and procedures connected with measurement of the primary variable.

Safety Population

Safety Population consists of all subjects who received any amount of either product, and on whom any post-randomization safety information is available.

2. Statistical Methods

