2.1 General Approach

The primary and secondary endpoints will be analysed for both ITT and PP population. Safety parameters will be analysed for Safety population. All data will be summarised by study group, visit and/or study week as specified in the study objectives.

For nominal variables, counts and percentages will be presented. The denominator for each percentage will be the number of participants within the study group at that visit unless otherwise specified.

For interval variables, the arithmetic mean, standard deviation, median and min-max range will be presented to two decimal places. This will be accompanied by the number of participants included in the analysis for that time point.

Changes in interval endpoints from pre-supplementation will be calculated as:

$$\text{Change to } V_i = \text{Value at } V_i - \text{Value at } V_{\text{pre-supplementation}}$$

P-values will be rounded to three decimal places. P-values less than 0.001 will be reported as <0.001. P-values less than or equal to 0.05 will be considered statistically significant. All analyses will be performed using R Statistical Software version 3.6.1 (R Core Team, 2019) for Microsoft Windows.

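### SAP 2.4.1 permits LOCF in the ITT crossover analysis with no limit to the same period; where it is used, early period-2 losses score the second product as no change, with a small effect for plausible losses

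*SAP*

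**What the plan says.** SAP 2.4.1 says of the ITT set: "Missing values in the intention-to-treat analysis will be imputed using the last available value" (LOCF) "or multiple imputation methods as appropriate". It gives no criterion for choosing between the two methods, no period boundary, and no rule for a missing Visit 6 value. For the other sets it says: "No imputation will be performed for missing values in the per protocol or the safety populations". Protocol 11.3 offers the same choice of methods, also without a period limit, but applies it more widely: "Missing values in the intent-to-treat and per protocol analyses will be imputed using the most recent previously-available value".

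Four other provisions determine what LOCF would do:

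- SAP 1.9 defines ITT as "all subjects who received either product, and on whom any post-randomization efficacy information is available", so a participant with data from one period only stays in.
- SAP 2.1 ("Changes in interval endpoints from pre-supplementation will be calculated as") subtracts the pre-supplementation value from the value at the visit. Protocol 9.8 labels Visit 6 the period-2 baseline.
- Protocol 8.5 says: "In both study periods, on day 1 only the evening dose will be administered". The Day 1 clinic sample therefore precedes the first dose of that period.
- SAP 2.2.1 plans a repeated-measures mixed model for the primary outcome: "The model will include treatment, visit number, sequence and period as fixed effects and subject as a random effect".

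**The concern.** In a crossover, the last available value may belong to the wrong treatment state. A period-2 baseline carried to Day 8 records no response to a product the participant may barely have taken. A period-1 value carried over the washout mixes the two products. Either can move the ITT estimate of the primary treatment difference, and with 18 participants each affected person carries 1/18 of the weight. Two permitted methods that can give different answers, with no rule for choosing, also leave the primary analysis under-specified.

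**Working it through.** **Inputs.** 18 participants, 9 per sequence; difference 8.7 pMol/mg protein; SD 11.04; 5% significance; 80% power; 20% loss to follow-up (all protocol 11.1). Withdrawn participants are not replaced (protocol 7.4). The number and timing of losses and the comparator change are my assumptions.

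**Reproducing the plan's figure.** The protocol does not say what kind of SD 11.04 is. Taken as the SD of the within-person difference, a two-sided paired t test has 77.8% power for 8.7 with 14 completers and 81.0% with 15. Then 15 × 1.2 = 18, the stated size. Taken as a within-subject SD (difference SD √2 × 11.04 = 15.6), 28 completers would be needed. I use the first reading.

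**What LOCF does, by time of loss.**

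- *Between Visits 6 and 7:* the untreated Day 1 value fills Day 8, so the second product's change is exactly 0.
- *After Visit 7 or 8:* a Day 3 or Day 5 value, from a visit one hour after dosing (protocol 9.4, 9.5, 9.9, 9.10), replaces a sample due 2 hours after the meal on Day 8 (protocol 9.6, 9.11).
- *During washout:* the change is again 0, but only if LOCF also fills Visit 6, which the SAP neither states nor excludes.
- *Visit 6 alone missing:* if LOCF fills it, an on-product Visit 5 value becomes the baseline. With no comparator change, each such RiaGev-first participant adds 8.7/18 = 0.48, away from the null.

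**Bias for losses before Visit 7.** Let a = RiaGev-first lost, b = comparator-first lost and c = comparator change, with no carryover or period effect and losses unrelated to outcome. A lost RiaGev-first participant contributes (8.7 + c) − 0. A lost comparator-first participant contributes 0 − c. All others contribute 8.7. Averaging the two sequence means gives

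bias = (−8.7b + c(a − b))/18.

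Coverage is from 40,000 simulated trials per case on change scores.

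| Lost (a, b) | Estimate, c = 0 | Coverage | Estimate, assumed c = +4 | Coverage |
|---|---|---|---|---|
| 1, 1 | 8.7 − 8.7/18 = 8.2 | 95% | 8.2 | not shown |
| 2, 2 | 8.7 − 17.4/18 = 7.7 | 94% | 7.7 | not shown |
| 0, 4 | 8.7 − 34.8/18 = 6.8 | 90% | 8.7 − 50.8/18 = 5.9 | 85% |
| 4, 0 | 8.7 | 95% | 8.7 + 16/18 = 9.6 | 94% |

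At (1, 1) the shift is 0.48 against a standard error (SE) of 2.54, about 0.2 SE. At (0, 4) with c = 0 the LOCF SE is 2.53 and the estimator's actual spread 2.44, so coverage falls because of bias and not because the SE is too small. For that case coverage is 78% if the SD is 5.5 and 92% if it is 15.6.

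**Later losses.** If the Day 5 effect is 75% of the Day 8 effect (assumed) and c = 0, a loss after Visit 8 carries a quarter of the bias: 8.5 for (2, 2) and 8.2 for (0, 4).

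**Type I error.** With four lost from one sequence, change scores give 5%, 6% and about 10% at c = 0, +4 and +8. A mixed-model simulation at (4, 0) gives 3.6% at c = +4 and 10.0% at c = +8. With even losses, change scores give 4% to 5%.

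**Observed values only.** A mixed model fitted without imputation to Days 3, 5 and 8 gave Day 8 estimates of 8.60 to 8.92 across these loss patterns, with coverage of 95.5% to 97.2% (600 trials per case). LOCF in the same model gave 7.78 at (2, 2) and 6.84 at (0, 4) with c = 0, close to the formula. That simulation assumed effects of 50%, 75% and 100% on Days 3, 5 and 8, a between-person SD of 10 and a residual SD of 5.52. It included treatment-by-visit and subject-by-period terms. Whether the SAP model needs a treatment-by-visit term is a separate question and no part of this point.

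**The case against.** The case for leaving the text alone has real force.

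- **It is conditional.** Multiple imputation is equally permitted, so nothing goes wrong unless LOCF is chosen. This stands. A reader might infer that the SAP commits the trial to a biased primary analysis; it does not.
- **The large figures are extreme.** The 20% allowance is 3.6 people over the whole study, and four losses is 22%. If four losses fall at random across sequences, all four are comparator-first with probability 126/3060, about 4%. This also stands.
- **Other provisions limit missing data.** Protocol 7.4 asks for end-of-treatment evaluations at withdrawal where possible, and protocol 10.2.2 keeps some withdrawn participants attending visits. The SAP's per-protocol analysis is not imputed and could expose an artefact. These reduce exposure, but they do not correct an ITT estimate once LOCF has been applied.
- **The planned model itself was not simulated under LOCF.** Neither the change-score estimator nor the mixed model above matches SAP 2.2.1 term for term. The sizes are therefore indicative, although the two approaches agree closely.
- **A narrower remedy exists:** a selection rule plus a bar on cross-period carry-forward. That would close the worst gap, but it would still let a Day 3 or Day 5 value stand in for Day 8.

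The protocol–SAP difference on per-protocol imputation might look like a second serious fault. It is minor for the primary outcome, because per-protocol participants must complete the visits and procedures for that variable (protocol 11.2, SAP 1.9).

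**Conclusion.** The point holds as a gap in specification with a permitted option that can bias the result. For plausible losses the effect is small: 8.2 instead of 8.7 with one early loss per sequence. It reaches 6.8 with 90% coverage when four comparator-first participants are lost before Visit 7 and the comparator does nothing.

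Two stronger readings should be resisted. LOCF does not always bias the estimate: RiaGev-first losses cause none if the comparator has no effect, and they inflate the estimate only if NAD+ rises on comparator. Nor is there general type I inflation: a material rise, to about 10%, needs one-sided losses and a comparator change of about +8, nearly the whole design difference. Nothing in the documents supports a change of that size.

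All sizes rest on 11.04 being the SD of the within-person difference, on assumed losses, and on no carryover or period effect.

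**What to change.** Before unblinding, revise SAP 2.4.1 as follows:

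1. Delete LOCF. Fit the planned mixed model to all observed ITT values without imputation. This is valid under missing at random if the mean and covariance model is adequate.
2. Keep multiple imputation as a sensitivity analysis only, with its model specified in advance.
3. State that no value is carried across periods, into a missing Visit 6 baseline, or from an earlier day to Day 8.
4. Reconcile protocol 11.3 with SAP 2.4.1, on the ITT method and on per-protocol imputation.

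The statistical cost is a somewhat wider interval. With four lost evenly, the SE is about 2.4 instead of 2.2 in the mixed model (power 92% either way), or 2.9 instead of 2.5 on completers' change scores (77% against 83%, with no comparator change). In the mixed model, one-period participants still contribute.

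The administrative cost is a dated SAP revision, with enrolment of 18 already reported in SAP 1.8, and a documented amendment to protocol 11.3 (protocol 11.5) that may need IRB review (protocol 9.16).
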